**Table 4 Delayed Free Recall (DFR) (Free and Cued Selective Reminding Test -FCSRT)**

**Sample size dimensions for a case-control unpaired study**

---

For:

Level of bilateral confidence (1-alpha)	99.9
Potency (% possibilità di individuazione)	99
Ratio controls-cases	1
Hypothetical proportion of controls with exposure	29
Hypothetical proportion of cases with exposure	81
Minium Odds Ratio to identify:	10.44

---

	Kelsey	Fleiss	Fleiss con CC
Sample size – Cases	58	51	55
Sample size - Controls	58	51	55

---

Sample Size- total  
sample

116

102

110

---

**Table 5. EEGSample size dimensions for a case-control unpaired study**

For:	Level of bilateral confidence (1-alpha)	99.9	
	Potency (% possibility of identification )	99	
	Ratio controls-cases	2	
	Hypothetical proprtion of controls with exposure	36.4	
	Hypothetical proprtion of cases with exposure:	87.5	
	Odds Ratio minimo estremo da rilevare:	12.23	
	Kelsey	Fleiss	Fleiss con CC
Sample size – Cases	46	38	41
Sample size - Controls	91	75	81
Sample Size- total sample:	137	113	122

It is not possible to apply an estimate of sample size to a pair of biomarkers as there are no specific data in the literature for the 2 couples with the highest sensitivity values previously reported (table 1). It should be noted that -as will be reported in the next paragraph- it is necessary to capture the full data set in order to have the number of cases which convert and do not convert to Alzheimer’s dementia for each of the 4 combinations of a biomarker pair (++; +-;+;- -). On the basis of relevant literature, using two specific approaches for sample size calculation for a single biomarker and estimating an approximate 20% drop-out rate for various reasons (death, severe neurodegenerative disease, dropout for poor compliance) during the follow up, a sample size of 400 patients with MCI is considered sufficient to highlight a biomarker or a pair of biomarkers with such a level of accuracy as to trigger the decision to prescribe a new anti-dementia medicinal product.

### 3.10 Statistical Analysis

Statistical analysis will be carried out following three areas:

1. Preparation of contingency tables for each of the seven biomarkers (MMSE; FCSRT; CSF CSF tau and p-tau/ABeta; F)FDG-PET; ApoE4; EEG) and processing parameters of sensitivity, specificity, positive predictive value and negative predictive value and overall accuracy. We will also calculate the positive and negative likelihood ratios (LR). The related 95% CI for each of these parameters shall also be calculated. The results will be compared with the positive and negative LR values, which are considered the gold standard for the placing on the market of a diagnostic test. (Jaeschke R, Guyatt GH, Sackett DL 1994)(see below).

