### **Inclusion criteria:**

- Age between 50 and 85 years
- Age and education corrected Mini Mental State Examination score equal or higher than 24/30
- Clinical Dementia Rating (CDR) global score of 0.5

a) concerns about cognitive modifications, expressed as subjective complaints by the subject, or an impression by a close acquaintance or an expert clinician;

b) defective performance with reference to age and education matched controls in one or more cognitive domains (memory, executive function, attention, language, visuospatial function): if repeated assessments are available, evidence of performance decline;

c) preserved functional autonomy: the subject remains fully independent, even if specific performances may be slower, less efficient than the usual level, with occasional errors;

d) no dementia: the cognitive modifications do not significantly hamper social functioning or work.

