#### Secondary Endpoints

Evaluation of cost/benefit ratio of individual biomarker or combination of biomarkers compared to their accuracy to predict progression from MCI to AD and their financial sustainability, availability in the country and non-invasiveness for patients.

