**Table 6. Interpretation of likelihood ratios**

Likelihood ratio Positive	Likelihood ratio negative	Changes in probability of the condition	Results
> 10	< 0.1	Large	Conclusive
5–10	0.1–0.2	Moderate	Moderately useful
2–5	0.2–0.5	Small	Sometimes useful
< 2	> 0.5	Tiny	Rarely useful
1	1	No change at all	Not useful

*(\*)Modified from: The investigation and management of the small-for-gestational-age fetus Royal College Obstetricians and Gynecologists - RCOG Guideline No. 31 November 2002*

2. For the two biomarkers with the highest sensitivity value we will proceed with an assessment in parallel with a mode "OR". Please note that in this study we use biomarkers in parallel in order to improve the overall specificity with respect to the use of every single biomarker. This implies that the purpose of the study is to develop an organizational model capable of identifying those subjects with MCI with the highest risk of converting to Alzheimer's disease (low percentage of false negative). Consider this theoretical example ([http://www.quadernodiepidemiologia.it/epi/screen/tst\\_com.htm](http://www.quadernodiepidemiologia.it/epi/screen/tst_com.htm)) which will be replicated with data captured in this study. Contingency tables can be set up separately for each of the 2 tests to calculate their sensitivity and specificity.

Compared to using a single test, in the case of interpretation «OR» it is less likely to miss a person with MCI converting to Alzheimer's dementia. However, there will be a low percentage of false negative, i.e. of subjects with AD at the end of the study but with biomarker negative at baseline. With this mode we might get an increase in sensitivity at the expense of specificity. In the case of interpretation «AND», it is easier to miss subjects with MCI converting to Alzheimer's disease, but there is a lower probability that a person with MCI is classified as a subject that will convert to Alzheimer's disease. Specificity increases at the expense of sensitivity.

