3. Cox logistic regression models will be performed that will help to identify the best pattern of variables for a subject with MCI candidate for conversion to Alzheimer's disease. For each patient included in the study, biographic and clinical information will be collected that will be used to construct multivariate models. In this regard, the months-person observation in the cohort will be calculated for each patient from the baseline visit to the end of the study or to his/her last visit or death.

Finally, in order to identify the combination of biomarkers to be proposed for selection of patients eligible for treatment with the new anti-dementia drugs, it shall be taken into account both costs and availability on the national territory of centres able to propose the diagnostic work-up, along with the level of invasiveness of the test. From a perspective of research in public health, the critical issues shall be carefully considered relating to standardization of analytical procedures for the determination of a biomarker, as documented by numerous reviews of the the Cochrane Collaboration. In this context the following solutions have been identified:

1. evaluation of "markers" shall occur in "expert centres" previously identified and connected through technology platform or receiving the samples stored at -80° C;
2. Training meetings shall be arranged for the panel of "expert centres" assessors in order to harmonize procedures, minimize the inter-rater variability and create a panel of "expert assessors" for each type of marker certifying the results for the individual subjects;
3. all information of the 400 subjects shall be blinded within a database provided by a professional biostatistical company approved by and under the supervision of the CC so that the assessors' panel of the individual exams is totally unaware whether MCI is 'Stable' or 'Converted' during follow-up. Only at the end of the Protocol will

the encrypted archive be opened and the diagnosis of all the NPT follow-up be coupled to each person;

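### Areas 1 and 2 of the analysis and the cost/benefit endpoint fix no comparison with the information collected at study entry, so they cannot show what a costly marker adds

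*Protocol*

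**What the plan says.** **Area 1** (protocol 3.10) plans "Preparation of contingency tables for each of the seven biomarkers", with sensitivity, specificity, predictive values, accuracy and likelihood ratios (LRs). "The results will be compared with the positive and negative LR values" that Table 6 sets out as general bands. MMSE and FCSRT stand in the same list as the other markers. The bracket omits volumetric MRI, but the count is seven and MRI is biomarker 7 in 3.3, so I take it as included.

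**Area 2** selects on the same stand-alone figures: "For the two biomarkers with the highest sensitivity value we will proceed with an assessment in parallel with a mode" of OR. On the protocol's own literature values (3.9, Table 1) the pair with the highest sensitivities is FCSRT and EEG.

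**Area 3** is multivariable: "Cox logistic regression models will be performed that will help to identify the best pattern of variables", and "biographic and clinical information will be collected that will be used to construct multivariate models". It names no reference model, no comparison with and without a marker, and no measure of what a marker adds.

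**The secondary endpoint** (3.7) is "Evaluation of cost/benefit ratio of individual biomarker or combination of biomarkers compared to their accuracy to predict progression", with no comparator.

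**Entry information** (3.2) includes "Age and education corrected Mini Mental State Examination score equal or higher than 24/30". FCSRT belongs to the battery used to define the objective-impairment criterion.

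**The concern.** The secondary endpoint is meant to inform which marker or combination the health service should use, weighing cost, availability and invasiveness. The unit costs in 3.14 run from 50 Euro for EEG to 1,000 Euro for FDG-PET. In a subject already assessed with MMSE and FCSRT, the useful question is how far a further test changes the predicted risk. A marker that largely repeats the memory score can have a respectable 2x2 table and still add nothing. One with the same table that carries different information can add a good deal.

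Selection by stand-alone sensitivity makes this worse. If the study reproduced the literature values, area 2 would examine FCSRT with EEG and would never combine CSF, FDG-PET, MRI or APOE4 with FCSRT. Predictive value is the natural scale here, because the synopsis wants the new drugs directed to subjects with a conversion risk of 90% or more.

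**Working it through.** **Reproducing the plan's figure.** Table 2 in 3.9 gives, for FCSRT, 59 true positives, 33 false positives, 14 false negatives and 81 true negatives. PPV = 59/92 = 0.641 and NPV = 81/95 = 0.853, matching the stated 0.64 and 0.85.

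**Inputs.** Conversion of 40% at 3 years is the protocol's working hypothesis (3.9). FCSRT sensitivity is 0.81 and specificity 0.71 (1.2). The other markers' sensitivity and specificity also come from 1.2.

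**Base.** PPV of FCSRT-positive = 0.4×0.81 / (0.4×0.81 + 0.6×0.29) = 0.324/0.498 = 65.1%.

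**Scenario A: the marker is redundant to FCSRT.** Its result depends on outcome only through FCSRT. Let a = P(M+ | FCSRT+) and b = P(M+ | FCSRT−). To reproduce the marker's own table we need

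- 0.81a + 0.19b = sensitivity
- 0.29a + 0.71b = 1 − specificity

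The determinant is 0.81×0.71 − 0.19×0.29 = 0.52. For MRI:

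- a = (0.71×0.60 − 0.19×0.25)/0.52 = 0.728
- b = (0.81×0.25 − 0.29×0.60)/0.52 = 0.055

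Both are valid probabilities. The factor a cancels in the PPV when both tests are positive, so PPV stays at 65.1% and the gain is zero. MRI's own LR+ of 0.60/0.25 = 2.40 is unchanged.

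**Scenario B: the marker is independent of FCSRT given outcome** (an assumption). PPV when both are positive = 0.4·0.81·se / (0.4·0.81·se + 0.6·0.29·(1−sp)). For MRI: 0.1944/(0.1944 + 0.0435) = 81.7%.

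| Marker | Sens / spec | a | b | Gain if redundant | PPV, both positive, independent | Gain (points, before rounding) |
|---|---|---|---|---|---|---|
| MRI | 0.60 / 0.75 | 0.728 | 0.055 | 0 | 81.7% | 16.7 |
| FDG-PET | 0.57 / 0.67 | 0.658 | 0.196 | 0 | 76.3% | 11.2 |
| APOE4 | 0.52 / 0.66 | 0.586 | 0.240 | 0 | 74.0% | 9.0 |
| CSF | 0.71 / 0.77 | 0.885 | −0.038 | infeasible | 85.2% | 20.1 |
| EEG | 0.87 / 0.64 | 1.056 | 0.076 | infeasible | 81.8% | 16.8 |

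For CSF and EEG one probability falls just outside 0 to 1, so full redundancy is not possible at those point values.

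Redundancy is not the same as maximal overlap of positives. Taking the smaller sensitivity and the smaller false-positive rate gives MRI a joint PPV of 0.4×0.60/(0.4×0.60 + 0.6×0.25) = 61.5%. That is below FCSRT alone, which a redundant marker cannot produce.

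**Sensitivity to conversion.** From 39% down to 26.6% (the protocol's literature range), the independence gains rise from 17.0 to 20.5 points for MRI, 11.4 to 13.3 for FDG-PET and 9.1 to 10.5 for APOE4.

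**Sensitivity to the base.** Add MMSE (0.57/0.86), again assumed independent given outcome:

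- FCSRT+ and MMSE+: PPV = 0.18468/(0.18468 + 0.02436) = 88.3%. A positive CSF then adds 7.6 points and MRI 6.4.
- FCSRT+ and MMSE−: PPV = 0.13932/(0.13932 + 0.14964) = 48.2%. CSF then adds 26.0 points and MRI 20.9.

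**The case against.** **Joint information is planned.** Area 3 fits multivariable models, 3.9 asks for converter counts "for each of the 4 combinations of a biomarker pair", area 2 discusses OR and AND rules, and the secondary endpoint covers combinations. A reader might infer that the protocol uses stand-alone accuracy in place of any joint analysis. The documents do not support that. What stands is narrower: none of these steps is tied to a reference model, and area 2 chooses its pair without using area 3.

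**Base covariates and discrimination indices belong in an SAP.** That is fair for the detail. But the likelihood-ratio benchmark, the pair-selection rule and the cost/benefit endpoint without a comparator are protocol text. An SAP that only specified the area 3 model would leave all three in force.

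**The PPV gains are not a pure measure of added value.** This is correct. Requiring two positives cuts the share called positive from 50% to between 23% and 34%, and sensitivity from 0.81 to between 0.42 and 0.70. Under the planned OR rule with FCSRT, PPV falls under independence: to 58.2% with CSF, 56.9% with MRI and 54.4% with EEG. The figures show that a stand-alone table does not determine the joint result; they do not forecast a benefit.

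**FCSRT may not be routine.** The protocol places it in the study battery and does not say that every MCI patient in ordinary care has it. The point therefore rests on information collected at study entry.

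**Conclusion.** The concern holds in limited form. Areas 1 and 2 judge markers by stand-alone accuracy, the cost/benefit endpoint has no reference strategy, and area 3 fixes no comparison with the entry information. On the protocol's own accuracy figures, one and the same table for MRI fits a gain over FCSRT of 0 or about 17 PPV points; for FDG-PET it is 0 or 11, and for APOE4 0 or 9. For CSF and EEG the independence gains are about 20 and 17 points, and a gain of exactly zero through full redundancy is just excluded at the point values.

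The sizes assume 40% conversion, the literature point estimates, an FCSRT-only base and both tests positive; the upper values also assume independence given outcome. Age, sex and education are not in the arithmetic, because the protocol gives no accuracy figures for them. A reader might infer that every costly marker could add either nothing or 17 to 20 points. That does not follow: FDG-PET, the dearest, reaches only 11 even under independence, and the gain shifts with the MMSE result.

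**What to change.** - **3.10, area 3:** set a base model of age, sex, education, MMSE and FCSRT. Add CSF, FDG-PET, MRI, EEG and APOE4 one at a time. For each, report the change in 3-year discrimination and in PPV at a fixed share called positive, with bootstrap 95% confidence intervals.
- **3.10, area 2:** choose the combination carried forward by this increment, not by stand-alone sensitivity alone.
- **3.7:** state the cost/benefit endpoint relative to the base model, for example extra cost per extra correctly classified subject.
- **3.10, area 1:** keep the stand-alone tables as description.

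The cost is analysis wording only. MMSE and FCSRT are recorded at entry and all markers are due within 60 days of T0 (3.5), so no further data are needed. The downside is that some markers will look less favourable than their stand-alone figures suggest.

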## SYNOPSIS

In the next 8 years a number of phase 2-3 trials will end up which utilize experimental drugs possibly *disease modifying* for Alzheimer Dementia. They target different disease stages: mild-moderate AD, 'early' AD, MCI prodromic to AD (MCI + for biomarkers heralding progression to AD), pre-symptomatic AD in pathogenetic gene mutation carriers of familiar AD forms. This dense clinical trials activity has triggered a fundamental question both from Patients and Scientific Communities and Health Authorities/Insurances: on which basis will the new drugs –if effective– be distributed to patients or at-risk population? This question mainly deals with the “MCI prodromal to AD” condition since the MCI population actually includes about 50% of those who will progress to AD (the real “prodromic to AD” MCI form) while the remaining 50% will never convert to AD. Since the new drugs –if effective– will carry both elevated unit costs and not marginal side-effects, they should be administered selectively to those MCI with a severely high risk of conversion (i.e. 90% or more) and particularly to those with a high risk of rapid conversion (1-2 years from diagnosis of the MCI condition).

The INTERCEPTOR project is focused on the prodromic AD condition (IWG2) or the MCI condition (NIA-AA) which form the neuropsychological point of view and is characterized by means of: cognitive questionnaire, screening test (MMSE), extended neuropsychological evaluation (incl. 2 episodic memory tests, language test, visuo-spatial abilities evaluation, behavioural scales Costa et al, 2017; Cerami et al, 2017), functional scales (Annex), full neurological examination. CDR must be 0.5. Atypical types of clinical presentations must be particularly considered (i.e. non amnesic debut) for a differential diagnosis where the role of biomarkers is pivotal.

In Italy, according to a recent study (Cohort Studies Memory in an International Consortium-COSMIC), an MCI prevalence of 5.9% has been evaluated in over 60 yrs population, with an increase of 4.5% between 60 & 69 yrs, of 5.8% between 70 & 79 yrs, and up to 7.1% in the 80 - 89 yrs range. On this epidemiological basis about 735.000 MCI cases are estimated for 2016 in the resident Italian population .

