### 3.9 Sample size

In order to calculate the sample size of this study which aims at identifying with the greatest possible accuracy the biomarker or set of biomarkers which could predict conversion from MCI to Alzheimer's dementia, the biomarkers are used as screening tests and then for their level of the sensitivity and specificity. The following table shows the sensitivity value pairs of seven biomarkers that were proposed in this study on the basis of evaluation of the literature reported in section 1.2 of the introduction.

**Table 1. Pairs of sensitivity values of seven biomarkers included in the study. The table shows that one pair of biomarkers (in bold and with an asterisk) is the combination of values of the highest sensitivity, including the use of**

DFR (FCSRT) and EEG. These two biomarkers were therefore taken into account for the calculation of sample size. Tables 2 and 3 show the values of sensitivity, specificity and positive/negative predictive value of the two biomarkers.

	MMSE	CSF p-tau	(  F)FDG-PET	DFR (FCSRT)	APOE4	EEG	Volumetric MRI
MMSE							
CSF p-tau	57/71						
(  F)FDG-PET	57/57	71/57					
DFR (FCSRT)	57/81	71/81	57/81				
APOE4	57/52	71/52	57/52	81/52			
EEG	57/87	71/87	57/87	81/87*	52/87		
Volumetric MRI	57/60	71/60	57/60	81/60	52/60		

Table 2 Data included in Grande's paper et al. submitted

Giulia	AD					
follow-up 2.5 anni	1	0				
DFR	1	59	33	92	sens	0.81
	0	14	81	95	spec	0.71
		73	114	187	vpp	0.64
					vpn	0.85

Table 3 Poil's study et al. 2013 (follow-up of 2 year) (EEG)

Poli 2013	AD					
follow-up 2 anni	1	0				
EEG	1	7	8	15	sens	0.88
	0	1	14	15	spec	0.64
		8	22	30	vpp	0.47
					vpn	0.93

In 2 years of the follow-up the conversion rate from MCI to AD is 26.6% (8/30). In summary, after a follow-up of about 2.5 years, the prevalence of AD in a cohort of patients with MCI ranges from 26.6% to 39%. Based on these data, it was decided to adopt 2 approaches, one based on the methodological work of Bujang & Adnan (Requirements for Minimum Sample Size for Sensitivity and Specificity Analysis. J Clin Diagn Res. 2016 Oct; 10 (10): YE01-YE06), the other using the logic of a case control study, in which the cases are represented by patients converting to Alzheimer's disease, while the control is represented by patients with MCI. In the latter case an OR was

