calculated between the biomarker and positive AD presence. In detail, the first approach allows us to predict a number of patients with MCI ranging from 78 to 388 in the hypothesis of a prevalence of 40% Alzheimer Dementia after 3 years of follow-up and a sensitivity value (working hypothesis) of 80-90% for an individual biomarker with a potency of about 81% and a p value lower than 5% (see below-from Bujang & Adnan 2016).

n (Sensitivity)						
Prev	H 0	H 1	Power	p-value	N1	N
40%	0.70	0.80	0.818	0.044	155	388
40%	0.70	0.90	0.807	0.048	31	78
40%	0.80	0.90	0.819	0.040	107	268

In detail, the second approach, typical of a case control study, has allowed to estimate with a power of 99% and a p value of 0.001 the following patients with MCI, depending on the type of biomarker. For the purposes of this study, it was decided to use very high values for alpha and beta parameters in order to minimize the statistical error of the first and second kind, thus giving priority to the use of the data for a decision at an individual level.

OpenEpi software was employed to calculate data in the tables 2 and 3. Tables 4 and 5 show details of sample size for two separate biomarkers by highlighting the value of OR between biomarker positivity and onset of Alzheimer's dementia.

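### The likelihood-ratio yardstick and the OR rule in section 3.10 do not match the protocol's own rationale of selecting MCI subjects with a 90% or greater risk of conversion

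*Protocol*

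**What the plan says.** **Purpose.** The Synopsis says of the new drugs that "they should be administered selectively to those MCI with a severely high risk of conversion (i.e. 90% or more", with particular interest in rapid converters. Section 3.9 closes by calling 400 patients sufficient to find "a biomarker or a pair of biomarkers with such a level of accuracy as to trigger the decision to prescribe" a new medicine. Section 3.10 ends by choosing the combination to be proposed for selecting patients eligible for treatment.

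**Yardstick.** Area 1 of section 3.10 plans, for each marker, "processing parameters of sensitivity, specificity, positive predictive value and negative predictive value and overall accuracy", plus likelihood ratios, all with 95% CIs. It then states: "The results will be compared with the positive and negative LR values, which are considered the gold standard". Table 6 is a five-band scale whose top band is LR+ above 10 or LR- below 0.1, labelled conclusive.

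**Combination rule.** Area 2 says: "For the two biomarkers with the highest sensitivity value we will proceed with an assessment in parallel", using OR, so that a subject is positive if either marker is positive. AND is described but not chosen. Area 3 adds regression and multivariable models with no limit on the number of markers, and with no risk cut-off.

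**Conversion rates.** Three are given:
- Section 3.9 sizes the study "in the hypothesis of a prevalence of 40% Alzheimer Dementia after 3 years of follow-up".
- The same section says of its two source studies that "the prevalence of AD in a cohort of patients with MCI ranges from 26.6% to 39" per cent.
- The Synopsis says "the MCI population actually includes about 50% of those who will progress to AD", with no time limit.

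**The concern.** A decision to prescribe rests on the risk in subjects who test positive, which is the PPV. A likelihood ratio becomes a risk only once a conversion rate is supplied, and Table 6 supplies none. A rule could therefore sit in the top band and still fall short of the risk that the protocol gives as the reason for the study.

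The OR rule raises a separate problem. It widens the positive group, so it finds more converters but dilutes the risk among positives. That suits the aim of missing few converters, which area 2 also states. It works against picking out a very high-risk group. Area 2 is inconsistent on this: it says parallel use is meant to improve specificity, then says that OR gains sensitivity and loses specificity.

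At stake is whether the conclusion on treatment eligibility answers the question that the Synopsis poses.

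**Working it through.** **Reproducing the protocol's figures.**
- Sample size: an exact two-sided binomial test of sensitivity 0.70 against 0.80 with 155 converters gives power 0.818 and alpha 0.044. 155/0.40 = 387.5, rounded up to the stated 388.
- Section 3.9, Table 2: LR+ = (59/73)/(33/114) = 2.79; odds 73/114 = 0.640; PPV = 2.79 × 0.640/(1 + 2.79 × 0.640) = 0.64, as stated.
- Section 3.9, Table 3: LR+ = (7/8)/(8/22) = 2.41; odds 8/22 = 0.364; PPV = 0.47, as stated.

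The route from LR+ to PPV therefore returns the protocol's own PPVs.

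**Step 1. LR+ of 10 against 90% risk.** With conversion rate p, LR+ needed = 9 × (1 − p)/p, and PPV at LR+ = 10 is 10p/(10p + 1 − p).

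| Conversion rate (source) | LR+ needed for 90% | PPV at LR+ = 10 |
|---|---|---|
| 26.6% (two years, section 3.9) | 24.8 | 78.4% |
| 39% (about 2.5 years, section 3.9) | 14.1 | 86.5% |
| 40% (three years, section 3.9) | 13.5 | 87.0% |
| about 50% (untimed, Synopsis) | 9.0 | 90.9% |

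**Step 2. Single markers.** From section 1.2, LR+ = sensitivity/(1 − specificity):
- MMSE 0.57/0.14 = 4.07
- CSF 0.71/0.23 = 3.09
- FCSRT 0.81/0.29 = 2.79
- EEG 0.87/0.36 = 2.42
- MRI 0.60/0.25 = 2.40
- FDG-PET 0.57/0.33 = 1.73
- APOE4 0.52/0.34 = 1.53

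At 40% conversion (odds 0.667) the PPVs include MMSE 73.1%, FCSRT 65.1% and EEG 61.7%.

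**Step 3. The OR rule, independence assumed.** Table 1 of section 3.9 names FCSRT and EEG as the most sensitive pair.
- Sensitivity = 1 − 0.19 × 0.13 = 0.975
- Specificity = 0.71 × 0.64 = 0.454
- LR+ = 0.975/0.546 = 1.79
- LR- = 0.025/0.454 = 0.054
- PPV = 54.4% at 40%, 64.1% at 50%, 39.3% at 26.6%

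In 400 subjects at 40% conversion, the rule flags 160 × 0.975 = 156 converters and 240 × 0.546 = 131 non-converters, and 156/287 = 54%. In Table 6 the LR- falls in the top band and the LR+ in the band below 2.

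**Step 4. The OR rule without independence.** The false-positive rate of an OR rule is at least that of its less specific member, here EEG at 0.36, and sensitivity is at most 1. So LR+ ≤ 1/0.36 = 2.78, and PPV ≤ 64.9% at 40% and 73.5% at 50%. With both specificities at their upper 95% limits (FCSRT 0.79, EEG 0.83), LR+ ≤ 1/0.21 = 4.76 and PPV ≤ 82.6% at 50%. Over all OR pairs of the seven markers, the loosest cap at point-estimate specificities is MMSE with CSF: LR+ ≤ 1/0.23 = 4.35, so PPV ≤ 81.3% at 50%.

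**Step 5. AND pairs, independence assumed.** LR+ is the product of the two.
- MMSE and CSF: 4.07 × 3.09 = 12.57; PPV 89.3% at 40%, 92.6% at 50%; sensitivity 0.57 × 0.71 = 0.405. It reaches 90% at a conversion rate of 41.7%.
- FCSRT and EEG: LR+ 6.75; PPV 81.8% at 40%; sensitivity 0.705.

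**The case against.** The best defence has four parts.

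**The 90% is rationale, not an endpoint.** The primary endpoint is comparative (which markers predict conversion more accurately), Table 6 is a graded scale, and nowhere is its top band said to trigger prescribing. This stands and limits the severity. But the protocol itself links the study to a prescribing decision and states no other risk mark.

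**PPV with a 95% CI is already planned.** True, so a reader could make the comparison. The protocol still directs the comparison to the LR scale.

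**At about 50% conversion, LR+ of 9 suffices.** Also true. That figure has no time limit, however, and the protocol assumes 40% for its three-year endpoint.

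**OR has a purpose.** It serves the aim of missing few converters, and its LR- of 0.054 shows that it would do so. That is a case for keeping OR for ruling out, not for using it to select a group at 90% risk.

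Three stronger readings are tempting but unsupported:
- *Markers are combined only in pairs.* Area 3 allows multivariable models of any size, and the aims speak of a set of biomarkers.
- *No pair can reach 90%.* This holds only for point estimates at 40% conversion under independence. The best AND pair misses by 0.7 points. Four AND pairs pass at 50%, and with MMSE specificity at its upper limit of 0.90 the best pair has LR+ 17.6.
- *Correlation between markers always makes AND rules worse.* For MMSE and CSF, a correlation of 0.2 among converters only raises LR+ to 13.96, while 0.1 in both groups lowers it to 9.13. Section 3.9 says that no pair data exist.

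**Conclusion.** The concern holds in two parts.

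The smaller part is the yardstick. LR+ above 10 is not tied to any conversion rate or to the 90% rationale. At LR+ = 10 the shortfall is 3 points at 40% conversion and 11.6 points at 26.6%, and it disappears at 50%. On the section 1.2 figures no single marker comes near LR+ = 10, so in practice this gap would matter for combinations.

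The larger part is the explicit combination rule. FCSRT OR EEG gives a PPV of about 54% at 40% conversion, lower than either marker alone. It stays well short of 90% at every conversion rate that section 3.9 or the Synopsis gives, whatever the dependence between the markers. The first figure assumes independence; the bound of 65% at 40% (74% at 50%) does not, but it does use the literature specificities. The EEG figures come from only 30 subjects, yet even at the upper specificity limits the bound at 50% is 83%. If other markers prove most sensitive in this cohort, the figures change, but the 81% cap at 50% covers every OR pair at the point estimates.

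This is a mismatch between the stated purpose and the planned analysis, correctable before analysis. It does not undermine the design or the data. Whether 90% is the right mark for treatment is not judged here; it is the protocol's own figure.

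**What to change.** In section 3.10:

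1. Judge markers, combinations and model-predicted risk by three-year PPV with 95% CI against the stated 90%, and report the share of converters captured at that risk. If 90% is not meant as the study's mark, say so and state what is.
2. Keep Table 6 as descriptive, or give beside it the LR+ that yields 90% at the observed conversion rate (13.5 if that is 40%).
3. Evaluate AND and multi-marker rules as well as OR, and tie the area 3 models to the same risk mark, with internal validation. Estimate joint accuracy from the study data, not by multiplying single-marker figures.
4. Correct the sentence saying that parallel use improves specificity, and state that OR serves to reduce missed converters.

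The cost is some rewording and extra analysis of data already being collected; cut-offs and validation details can go in the SAP. The downsides are a stricter yardstick, which the markers may fail, and more rules compared on the same cohort, which is why internal validation is needed.
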